To maximize retention of participants in the Aim 3 MRT, we will employ strategies that have been used in other EMA studies, including those conducted by co-I [name]. These strategies include participant training prior to beginning the TMI, which will ensure that participants are fully informed of the nature of the program and the level of responsibility that is required, personal contact with study personnel via phone prior to enrollment and upon completion of the TMI, tailored feedback on EMA completion rates sent via text or email (depending on participant preference) at the end of every week of the 4-week TMI period, and bonus incentives for compliance. In addition, we will monitor compliance with EMA every 3 days during the Aim 1 EMA data collection and the 4-week pilot MRT, and for those clients who do not respond to any EMA surveys in a 3-day period, the RA will send reminder text messages.

Eligibility Screening

Participants will complete eligibility screening online via a secure Qualtrics survey that contains the eligibility screen.

Technology Platforms for Data Tracking, EMA and TMI Implementation

We will use Partnership to End Addiction's JITAI Master Platform for tracking participants through the study. For EMA and MRT data collection, we will use MetricWire's data collection app, Catalyst. Developed by MetricWire Inc., the MetricWire EMA system will collect the study's EMA survey data through the Catalyst EMA study app. Catalyst is secure and HIPAA compliant and does not have any associated conflicts of interest. Participants will install the Catalyst app on their own smartphones. Data on the participant's smartphone are

synced (encrypted in-transit) to the server and wiped from the mobile device when a connection is available. When the participant's device is not connected to the internet, data are stored (encrypted) on the device. When offline, the app/server periodically checks for a connection in the background and performs the sync/wipe of any response data. This allows triggers and data collection to occur offline while minimizing the amount of time data are stored on the device.

All participant generated data are stored in production information systems in hosted (cloud) environments and are not permitted to be stored on locally managed electronic devices such as MetricWire workstations.

User Identification

- All critical Information systems require a unique and valid User Login ID and password for each individual user.

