Step 1: Baseline Assessment. Participants who sign informed consent will be asked to complete a Baseline Assessment via Qualtrics. Participants will be sent a secure link to the Qualtrics survey via text or email. The Baseline will take approximately 30 minutes to complete and will include questions about demographics, parenting, mental health, stress and coping, motivation, and drinking and other substance use.

[figure not shown]
Step 2: Catalyst Training. Following completion of the Baseline, participants will participate in a one-on-one 15-minute training session with the RA via Zoom to provide training on how to download and use the Catalyst app. In order to avoid fraudulent participants, participants will be asked to turn on their camera for 1 minute of the training, after which they will be allowed to turn off their cameras for the remainder of the training if that makes them more comfortable. Participants who complete both the baseline survey and the Catalyst training session will receive a \$25 Amazon gift card upon completion of the Catalyst training session.

Step 3: 28-day MRT. After completing the training, the TMI sequence of EMAs and TMI text messages will begin as described below and will last for 28 days.

TMI Sequence and Randomization

Upon completion of the Catalyst training, the TMI sequence of EMAs and TMI component delivery will begin (see Figure 2).

Figure 2. TMI Sequence

There will be two decision points per day. Decision points will be randomly selected within a 12 hour window starting at the participant's pre-selected start time. There will be at least 4 hours between the two decision points. At each decision point, participants will receive the "decision point EMA." Upon completion of the decision point EMA, participants will be randomized to one of three options: (1) a maternal-focused message (.40 probability); (2) a drinking-focused message (.40 probability); or (3) no message (.20 probability). Fifteen minutes after randomization, participants will receive the "proximal outcome EMA." This sequence will repeat 2 times per day, at each decision point. Participants will also be sent a "morning survey" each morning within 30 minutes of their selected start time that will ask questions about the prior day. After each survey prompt, the survey will be

available for up to 60 minutes, with 2 reminder prompts sent (every 20 minutes). Surveys that are not completed within the 60 minute window will expire.

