Additionally, an optional “nighttime sequence” will become available nightly at 10 PM. The nighttime sequence will be optional with no prompt sent to avoid disturbing participants during the night. The reason for the nighttime sequence is to enable data collection and message receipt during the night when participants may be awake with their baby, which may be times of high risk for new mothers.

The questions asked in each survey are shown in Tables 4-6 below. Completion of the morning survey should take approximately 2 minutes. Completion of each EMA survey should take approximately 1 minute.

We will use the following procedures to encourage and monitor compliance: (1) one-on-one training prior to the start of data collection; (2) availability of technical support; (3) daily reminders to complete surveys; (4) bonus incentives; (5) outreach to participants who did not complete any EMA surveys 3 days in a row. If 3 days pass without any EMA responses, participants will receive an automated text message reminding them to complete the surveys. The reminder message will be sent once per day for 5 days. If there is still no response, the participant will be considered dropped from the study.

In order to ensure participants are adequately supported during the study, we will provide information on how to obtain additional support for drinking (support hotlines). This information will be available within the Catalyst app at all times for participants to access if needed; (3) provide all participants with a list of local resources at the outset of the study.

MRT Measures

Baseline Assessment:

Construct	Measure
Demographics	Questions developed for study
Drinking Self-efficacy	Drinking Refusal Self-Efficacy Questionnaire-Revised ⁷
Alcohol and Drug Use history	NIDA modified ASSIST ⁸ NIAAA Recommended Alcohol Questions ⁹
Alcohol and Drug Use	Timeline Follow Back ¹⁰
Motivation/Readiness for Change	Maternal Motivation Scale ¹¹
Postpartum Depression	Beck Depression Inventory ¹²
Maternal Self-efficacy	Karitane Parenting Confidence Scale ¹³
Trauma History	ACE 10 item Questionnaire ¹⁴
Maternal Attachment	Infant Bonding Scale ¹⁵
Fatigue	Fatigue Assessment Scale ¹⁶
Stress	Perceived Stress Scale-4 ¹⁷
Drinking Motives	Drinking Motives Revised Questionnaire ¹⁸
Coping self-efficacy	Coping Self-Efficacy Scale ¹⁹
Social Support	SSQ6 ²⁰
Digital Literacy	Media and Technology Usage and Attitudes Scale ²¹

Feasibility and Acceptability. Feasibility and Acceptability Outcomes:

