Study participants will receive incentives to participate in the study. Incentives will be received in the form of gift cards to Amazon. Incentives will be provided for completion of the Aim 3 baseline assessment and Catalyst training, and the Aim 3 follow-up survey and qualitative interview. Reimbursement for the Aim 3 baseline assessment and Catalyst training will be provided upon completion of the Catalyst training. Reimbursement for the Aim 3 EMAs (as part of the MRT) will be provided at the end of the four-week testing period of the TMI, and reimbursement for the follow-up survey and qualitative interview will be provided upon completion of each survey. Gift cards will be provided via email or text. Participants who withdraw from the study prematurely will receive reimbursement for all study components they completed. Participants will receive \$25 for completing the baseline and training, \$25 for the follow-up, and \$25 for the qualitative survey. Participants will receive \$0.50 for each EMA survey they complete, plus a \$20 bonus for completing 50% of surveys and a \$30 bonus for completing 80% of surveys. The bonus incentives for completing 50% and 80% of required EMA surveys are used routinely in EMA studies to boost compliance, and have been used in EMA studies with postpartum women (for example: ³⁸), and are not thought to be coercive given the relative low amount of money provided. [name] (study Co-I) has used these methods in prior studies of young adult smokers, with bonus incentive rates up to \$60 (see ^{22,32,39}). Due to an increase in fraudulent participants, we have added language to the consent form that states that participants who are determined to have entered the study fraudulently will not be compensated and will be unenrolled from the study.

RISKS AND BENEFITS

Potential Risks for Participants

This study presents no greater than minimal risk to participants. Potential risks for study participants include risks associated with assessment questions, general risks associated with confidentiality, mandated reporting of child abuse and neglect, and specific risks associated with the use of cell phones to deliver an intervention for risky drinking. Each of these risks is described in the following sections.

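### After 8 days without an EMA response a woman is classed as out of the study; read literally, this ends her follow-up survey and interview although she has not withdrawn consent

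*Combined protocol and SAP*

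**What the plan says.** The rule stands in the compliance procedures under TMI Sequence and Randomization. Outreach begins after three silent days: "If 3 days pass without any EMA responses, participants will receive an automated text message reminding them to complete the surveys". Then "The reminder message will be sent once per day for 5 days". Then "If there is still no response, the participant will be considered dropped from the study". The last sentence refers to the study as a whole, not to EMA or to messages.

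The MRT itself is set in Procedures, Step 3: "the TMI sequence of EMAs and TMI text messages will begin as described below and will last for 28 days". On intensity, "There will be two decision points per day". Randomization happens only once a decision point EMA is completed.

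Participant Incentives lists two later components at $25 each, and says that "reimbursement for the follow-up survey and qualitative interview will be provided upon completion of each survey". Women who withdraw early are paid for what they finished. That section does not say whether later components are still offered to them. Retention Strategies plans "personal contact with study personnel via phone prior to enrollment and upon completion of the TMI".

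**The concern.** EMA silence is treated as leaving the study, although the woman has not asked to leave. The follow-up survey and the interview do not depend on EMA, yet a woman who is out of the study would not normally be approached for either.

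The stated primary goal of the pilot is feasibility and acceptability of MRT methods. Women who stop answering know most about burden. The platform records show when they stopped but not the reason. The burden items sit in the final daily diary, which a silent woman does not answer, so the follow-up survey and interview are the planned contacts at which she could still be heard. If she is not invited, both describe mainly women who tolerated the method.

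A gap in responding also gives no design reason to end participation. A missed decision point simply produces no randomization, and a mother a few weeks after birth might fall silent for a week and then return.

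**Working it through.** The plan gives no figure to reproduce here; it states that no formal power analysis was done. The check is a day count and a comparison of sections.

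**Inputs.** Silent days before outreach: 3. Daily reminders: 5. MRT length: 28 days. Decision points: 2 per day. Prompted surveys: up to 5 per day (1 morning, 2 decision point, 2 proximal outcome). The 5 is an assumption, because a proximal outcome EMA follows only a completed decision point EMA and the optional nighttime sequence is left out.

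**Time to the drop.** 3 + 5 = 8 days, or 2 + 5 = 7 if the first reminder goes out on the third silent day. Eight days are 8/28 = 28.6% of the MRT, 8 × 2 = 16 of 56 decision points, and up to 8 × 5 = 40 of 140 surveys.

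**Who can be caught.** The last day on which silence can begin and still complete the rule is 28 − 8 + 1 = day 21. Any EMA response in the window avoids the drop.

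**What remains after the drop.** If the last response is on day d, the drop falls at the end of day d + 8. That leaves 20 − d days and 2 × (20 − d) decision points. The last two columns give the highest possible share of surveys completed.

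| Last response (d) | Dropped after day | Days left | Decision points left | Ceiling if drop is final (d/28) | Ceiling if she may resume (20/28) |
|---|---|---|---|---|---|
| 4 | 12 | 16 | 32 | 14.3% | 71.4% |
| 7 | 15 | 13 | 26 | 25.0% | 71.4% |
| 13 | 21 | 7 | 14 | 46.4% | 71.4% |

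In surveys, the first row with resumption is 4 × 5 + 16 × 5 = 100 of 140. The 71.4% does not depend on the number of surveys per day. It is a ceiling: it needs full response on every day outside the gap.

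**Is a dropped woman sent to follow-up anywhere?**
- Procedures has three steps and ends with the MRT. It contains no follow-up step for anyone, so it neither includes nor excludes her.
- The closing phone contact in Retention Strategies is tied to completion of the TMI. This may mean finishing the programme or reaching the end of its period; only the second reading would include her.
- Participant Incentives puts no EMA condition on payment for follow-up or interview, but does not say who is invited.

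No section tells staff to contact her, and none tells them not to.

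**Number of women.** The documents give no expected rate. If 10% to 30% met the rule (assumption), that would be 0.10 × 50 = 5 to 0.30 × 50 = 15 women.

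**The case against.** A reader might infer that these women are certainly lost to follow-up and barred from returning. The documents do not support that. They nowhere say that prompts are switched off, invitations withheld or a return refused. What they contain is an unqualified label that has this effect if followed literally.

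Four other strong readings also fail:
- *Follow-up would hear only from women who tolerated the method.* Women who answer rarely, and women who fall silent on day 22 or later, are not caught on the 8-day count.
- *The drop forfeits the 50% bonus.* Participant Incentives ties the bonus only to the share of surveys completed.
- *The rule causes the missing drinking data.* With a last response on day 4, days 5 to 28 (24 days) carry no report. Eight of those days precede the drop, and the other 16 are lost to the rule only if she would have resumed.
- *Follow-up results will be too favourable.* The content of the follow-up survey and interview is not described, and MRT Data Analysis uses neither.

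The feasibility analyses in MRT Data Analysis (recruitment time, enrolled versus declined, paradata, retention) can still be run with dropped women included. One could therefore call this a single undefined term.

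These limits stand and narrow the point. They do not remove it. Paradata cannot give a reason for stopping, and staff who follow the text have no instruction to seek one. If the sponsor already intends to follow these women, the text still has to say so.

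**Conclusion.** The concern holds as a cheap improvement. As worded, the rule turns 8 days of EMA silence starting by day 21 into exit from the study without withdrawal of consent. Read literally, it removes the woman from two components already planned and leaves no stated way back.

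The likely consequence is selective loss of follow-up and interview data among women who stopped responding, which would tilt acceptability findings toward those who continued. That direction is a plausible inference and cannot be measured from the documents. The size rests on the assumed 5 to 15 of 50 women and on the literal reading of the rule. The planned paradata analyses are not undermined.

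**What to change.** 1. In the compliance procedures, replace the drop with a status such as *classed as having stopped EMA*. Reserve *withdrawn* for women who ask to leave.
2. State that a woman who resumes within the 28 days is still in the MRT.
3. Add a step to Procedures: at the end of the 28-day period, offer the existing follow-up survey and qualitative interview to every randomized woman who has not withdrawn consent, whether or not she completed the TMI.

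Optional additions are one item on the reason for stopping, and the Timeline Follow Back (listed at baseline) at follow-up. The latter would rest on recall over the 28 days.

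The cost is protocol wording plus at most $25 + $25 = $50 per woman for components already listed for payment. For 5 to 15 women that is $250 to $750 if all take part. Some invitations will go unanswered.

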
The study has three primary aims:

Aim 1: Test and refine the proposed theoretical model via Ecological Momentary Assessment (EMA). This aim will refine the theoretical model underlying the TMI that specifies the impact of the proposed intervention components on the theoretical risk factors for postpartum RD, as well as decision rules for adaptive tailoring. Aim 1 work will include cellphone-based data collection using EMA with 30 women for 14 days to determine patterns and fluctuations of stress, negative mood, and self-efficacy in response to perceived sleep quality and baby irritability, and their impact on motivation, coping, and drinks per day.

Aim 2: Develop the components of an adaptive TMI aimed at reducing postpartum risky drinking. This aim will develop content and decision rules for adaptive tailoring that are consistent with Aim 1 results. TMI components will be based on evidence-based motivational and behavioral interventions for alcohol use and will be adaptively tailored to individual fluctuations in stress, negative mood, and self-efficacy. Components will be refined via iterative cycles of user feedback collected via focus groups with 30 women.

Aim 3: Conduct a pilot micro-randomized trial (MRT) to assess feasibility of design and methods in preparation for a future fully powered optimization trial. We will conduct a pilot MRT with 50 postpartum women with the primary goal of demonstrating feasibility and acceptability of MRT methods and the secondary goal of providing proof-of-concept data on the comparative impact of maternal-focused and drinking-focused messages on proximal (motivation, self-efficacy, and self-regulation) and distal (daily drinking) outcomes.

To achieve these aims, the study will apply the Multiphase Optimization Strategy (MOST) framework. Study activities comprise the Preparation Phase of MOST, and will proceed in three phases to achieve the three study aims. **Phase 1 (Aim 1)** (10 months) will include EMA with 30 women for 14 days aimed at refining the conceptual model and evaluating EMA feasibility. **Phase 2 (Aim 2)** (10 months) will develop TMI components, including message content and decision rules to guide adaptive tailoring of the TMI via an

iterative user-centered design process with 30 women. Phase 3 (Aim 3) (11 months) will consist of a pilot MRT with 50 women to examine feasibility of the MRT design and preliminary effects of the TMI components on the proximal and distal outcomes.

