Drawing from other EMA feasibility studies²²⁻²⁷, feasibility outcomes will include the percent of EMA surveys completed each day, each week, and at the end of the 14-day period; the percentage of each EMA measure completed; and the percentage of respondents who completed 50% and 80% of EMA surveys^{22,23}. Acceptability measures will be collected via a short text-based survey at the end of the 14-day EMA period and will include assessment of technical challenges, burden, emotional response, and overall satisfaction, using Likert-scale items from other EMA studies²⁴⁻²⁷.

Morning Survey Measures:

[Sent daily at participant-selected wakeup time.]

Construct	Items
EMA Burden/ Acceptability questions [include]	Retrospective questions 1=not at all, 7= very much Burden: 1. Answering to the questions disrupted my everyday life

in final daily diary at end of study]	
 2. The questionnaires on the phone stopped me from doing my usual activities 3. I found it embarrassing when the alarm sounded around other people 4. I enjoyed using the app 5. I found it stressful to use the app 6. Did your motivation to respond to the notifications decrease during the weeks? 7. How tiring was it to take part in this study? 8. Did the questionnaire become boring during the day? 9. Did you get irritation while filling in the questionnaire? 
Ease of use
 
 1. The questionnaires on the phone were easy to complete/ 2. At times I had to rush to complete the questionnaire on the phone on time 3. I found it easy to remember to carry the phone with me during the time of the study
How much time did you spend with your baby yesterday?	
 1. Most or all of the day 2. About half of the day 3. Less than half of the day 4. Evening and night only 5. None 6. Other 
 a. For "how much time did you spend with your baby yesterday" you selected other. Please write in your response below.
Prior night sleep ²⁸	
 1. How well did your baby sleep last night (0 = poor to 7 = excellent) 2. How well did you sleep last night [0 = poor to 7 = excellent]

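### The cumulative EMA completion rate and the acceptability survey are set at the end of a 14-day period, but the micro-randomized trial lasts 28 days

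*Combined protocol and SAP*

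**What the plan says.** The opening note of the combined protocol and SAP limits the document to Aim 3, the pilot MRT. Under MRT Measures, the Feasibility and Acceptability Outcomes paragraph uses a 14-day period twice:

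- The completion outcome is "the percent of EMA surveys completed each day, each week, and at the end of the 14-day period".
- For acceptability: "Acceptability measures will be collected via a short text-based survey at the end of the 14-day EMA period".

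The same paragraph lists the percentage of respondents who complete 50% and 80% of EMA surveys, with no window stated.

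Other sections give a different length for the MRT:

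- Procedures, Step 3: "the TMI sequence of EMAs and TMI text messages will begin as described below and will last for 28 days".
- Retention Strategies: women receive feedback on their completion rates "at the end of every week of the 4-week TMI period".
- Participant Incentives: payment for the Aim 3 EMAs follows the four-week testing period, and the bonuses use the same 50% and 80% thresholds.

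The only other 14-day period is in the description of Phase 1 (Aim 1): "EMA with 30 women for 14 days aimed at refining the conceptual model and evaluating EMA feasibility". The Morning Survey Measures table places a set of burden and acceptability items "in final daily diary at end of study".

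**The concern.** The 14-day period cannot be obtained from the Aim 3 schedule. It matches only Aim 1, whose purposes include EMA feasibility, so the wording looks carried over. That origin is an inference, and the inconsistency does not depend on it.

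Feasibility and acceptability are the pilot's primary goal. As written, the one cumulative completion figure describes half of the period women are asked to complete, and the acceptability survey goes out in the middle of the intervention. If response falls after day 14, the reported rate overstates completion over the whole MRT, and that rate would inform the design of the later fully powered trial. The plan treats such a fall as possible, since one diary item asks: "Did your motivation to respond to the notifications decrease during the weeks".

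The undefined window for the 50% and 80% outcomes adds to the problem. A reader could apply either 14 or 28 days.

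**Working it through.** **Stated lengths**

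| Section | Period |
|---|---|
| Study aims, Phase 1 (Aim 1) | 14 days |
| Feasibility and Acceptability Outcomes (under MRT Measures) | 14 days, twice |
| Procedures, Step 3 | 28 days |
| Retention Strategies | 4 weeks |
| Participant Incentives | four weeks |

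The MRT Data Analysis section names no 14-day point.

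**Scheduled prompted surveys per woman**

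Inputs from TMI Sequence and Randomization: two decision points a day, each with a decision point EMA and a proximal outcome EMA, plus one morning survey. The optional, unprompted nighttime sequence is excluded.

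- EMAs only: 2 + 2 = 4 a day. Over 14 days 4 × 14 = 56; over 28 days 4 × 28 = 112. For 50 women: 2,800 and 5,600.
- With morning surveys: 4 + 1 = 5 a day. Over 14 days 5 × 14 = 70; over 28 days 5 × 28 = 140. For 50 women: 3,500 and 7,000.

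Either way the 14-day rate covers one half. These are maxima for prompted surveys, because the sequence continues only after an answered decision point EMA: "Upon completion of the decision point EMA, participants will be randomized to one of three options", and the proximal outcome EMA follows 15 minutes later.

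**Completer thresholds (morning surveys counted)**

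- 50%: 0.5 × 70 = 35 surveys over 14 days; 0.5 × 140 = 70 over 28 days.
- 80%: 0.8 × 70 = 56 over 14 days; 0.8 × 140 = 112 over 28 days.

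**Effect on the reported rate, scheduled denominators**

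Let r1 and r2 be the completion rates in days 1–14 and 15–28, with equal scheduled counts. Then

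14-day rate − 28-day rate = r1 − (r1 + r2)/2 = (r1 − r2)/2.

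The documents give no rates, so these are assumptions:

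| r1 | r2 | 28-day rate | Excess of 14-day rate |
|---|---|---|---|
| 80% | 80% | 80% | 0 points |
| 80% | 70% | 75% | 5 points |
| 80% | 60% | 70% | 10 points |

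The extreme case is a woman who answers everything to day 14 and nothing afterwards: 100% at day 14, 50% at day 28.

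**Sensitivity: denominator is prompts actually sent**

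Assume the same completion rate p for every survey type. For EMAs only, 2 + 2p are sent and 2p + 2p² completed each day; morning surveys add 1 and p.

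- 80% then 60%, EMAs only: (2.88 + 1.92)/(3.6 + 3.2) = 70.6%, excess 9.4 points. With morning surveys: (3.68 + 2.52)/(4.6 + 4.2) = 70.5%, excess 9.5 points.
- 80% then 70%: (2.88 + 2.38)/(3.6 + 3.4) = 75.1%, and with morning surveys (3.68 + 3.08)/(4.6 + 4.4) = 75.1%, excess 4.9 points.

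The choice of denominator hardly changes the result.

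**The case against.** The strongest reply is that little is lost. Daily and weekly rates are also planned and, with their counts, give the 28-day rate directly. MRT Data Analysis examines response counts, message views, days of engagement and retention with no 14-day limit. The burden and ease-of-use items come at the end of the study, and Participant Incentives mentions a follow-up survey and a qualitative interview. The plan has no numeric completion criterion, so a day-14 figure could not reverse a prespecified decision. All of this stands, and it limits the harm to the cumulative rate and the survey timing. It does not remove the point: the analysis section names no whole-period completion percentage, and a survey sent at day 14 cannot be re-timed afterwards.

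A second reply is that the paragraph may be leftover Aim 1 text to delete or relabel, since other text from earlier aims remains in the document. But it stands under MRT Measures in an Aim 3 document, and deleting it would remove the MRT's stated completion-rate outcomes and its acceptability survey.

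A third concerns the figures. The rates are assumed, and the counts exclude the nighttime sequence. Nor do the documents say whether a woman counted as a dropout, after three silent days and five days of reminders, stays in the denominator; if she leaves it, the two halves are no longer equal. These limits are fair. They affect the illustration, not the mismatch.

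Finally, the text-based survey and the end-of-study diary items may be two instruments. Their different timing therefore needs clarifying and is not a proven contradiction.

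**Conclusion.** The concern holds and should be fixed. The paragraph ties two primary-goal measures to a period that is half the length of the MRT and is defined nowhere within it. Half of the scheduled prompted surveys fall outside the cumulative rate, whether or not morning surveys count. The resulting overstatement is half of any fall in response between the halves, given equal scheduled denominators; its actual size is unknown and may be zero. The conclusion that the periods disagree needs no assumption about response rates or about how the wording arose. Sample size, randomization and the effect models are not affected.

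**What to change.** In Feasibility and Acceptability Outcomes, change both 14-day references to the 28-day MRT period, and keep the daily and weekly rates. State that the 50% and 80% completer outcomes use the same 28-day window, which agrees with the four-week payment basis in Participant Incentives.

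Three clarifications belong in the same edit:

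- whether morning and nighttime surveys count as EMA surveys in these rates;
- whether the denominator is scheduled surveys or prompts sent, and whether dropouts stay in it;
- whether the text-based acceptability survey and the end-of-study diary items are one instrument or two.

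The cost is a few words and no new completion data. The completion figure may be less favourable. A survey at day 28 may miss women who stopped responding earlier, so the number answering it should be reported alongside the results.

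### Overall completion and the acceptability survey are timed to 14 days in a 28-day MRT, and the only acceptability items written out are asked once, on the last morning, and rate no messages

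*Combined protocol and SAP*

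**What the plan says.** The combined protocol and SAP is limited on its first page to Aim 3, which has the "primary goal of demonstrating feasibility and acceptability of MRT methods". Purpose of Pilot MRT extends acceptability to the messages as well as the methods.

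Two places under MRT Measures say how this is measured:

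- **Feasibility and Acceptability Outcomes.** Completion is the "percent of EMA surveys completed each day, each week, and at the end of the 14-day period". Then: "Acceptability measures will be collected via a short text-based survey at the end of the 14-day EMA period". These measures "will include assessment of technical challenges, burden, emotional response, and overall satisfaction".
- **Morning Survey Measures.** Nine burden items and three ease-of-use items, headed with a 1 to 7 scale, are to be included "in final daily diary at end of study".

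Step 3 gives the MRT a length of 28 days, and TMI Sequence and Randomization sets two decision points a day. A 14-day period belongs to Aim 1: "cellphone-based data collection using EMA with 30 women for 14 days".

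Each survey prompt is open for 60 minutes. After three days without any EMA response a woman gets a daily automated reminder for five days; if she stays silent, she is treated as dropped.

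Other contacts are named. Retention Strategies lists "personal contact with study personnel via phone prior to enrollment and upon completion of the TMI", and Participant Incentives pays $25 each for a follow-up survey and a qualitative interview. Their items, timing and recipients are not given. MRT Data Analysis covers recruitment, engagement and retention, and describes no acceptability analysis.

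**The concern.** Feasibility and acceptability are the main product of this pilot, and three features of the text weaken the acceptability half.

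1. **Period.** Two measures end at a time point that the MRT does not have. Someone following the text would send the survey, and close the overall completion rate, halfway through.
2. **Who answers.** The 12 items sit in one survey on one morning. If burden contributes to stopping, the women who found the study most burdensome are the least likely to be there, and the ratings would look too favourable. The planned logistic regression of retention will show who stopped, not how they rated the study.
3. **What is asked.** The items concern the questions, questionnaires, alarm, app, notifications, phone and taking part. None rates the maternal-focused or drinking-focused messages. The risk section names being triggered by messages as a possible harm and cites ratings of it from an earlier study, but no listed item asks women for such a rating here.

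**Working it through.** The plan states no figure for acceptability response, dropout or an acceptability threshold, and it ran no formal power analysis. There is therefore nothing to reproduce. The check compares the passages and uses simple counts.

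**Period covered.** Inputs: 2 decision points a day, each with two EMAs, plus one morning survey; 28 days.

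- Decision points: 2 × 28 = 56. By day 14: 2 × 14 = 28, and 28/56 = 50%.
- Scheduled surveys, leaving out the optional night sequence: 5 × 28 = 140, against 5 × 14 = 70. Counting EMAs only: 4 × 28 = 112, against 4 × 14 = 56. Either denominator is halved.

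**When the drop rule removes a woman before the final diary.** Assume the final diary is on the morning of day 28. Three silent days and five reminder days take 8 days, so the last response falls on day 28 − 1 − 8 = 19: silent on days 20 to 22, reminders on days 23 to 27. If the final diary falls on day 29, the limit moves to day 20.

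- Decision points passed by day 19: 2 × 19 = 38, and 38/56 = 68%.
- Expected messages of each type by then, if every decision-point EMA was answered: 38 × 0.40 = 15.2.

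So a woman can have had about two thirds of the intervention and be out of reach of the 12 items as written.

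**Items.** 9 + 3 = 12 written out; 0 rate the messages.

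**Uncertainty from missing answers.** With 50 women, a 1 to 7 scale and k missing, setting missing answers to 1 and then to 7 gives a range of width (7 − 1) × k/50 = 0.12k. The values of k are assumptions.

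| k missing (assumed) | Width of range for an item mean |
|---|---|
| 5 | 0.6 |
| 10 | 1.2 |
| 20 | 2.4 |

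Example with k = 10 and an assumed observed mean of 3.0: lower bound (40 × 3 + 10 × 1)/50 = 2.6; upper bound (40 × 3 + 10 × 7)/50 = 3.8.

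**The case against.** The strongest reply is that much of this is covered elsewhere, and several parts of it stand.

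- **Women who stop early.** A reader might infer that their views are lost altogether. The documents do not support that. The follow-up survey, the interview and the phone contact at the end of the TMI could reach them. What can be said is that content and recipients are not stated.
- **The second half of the MRT.** A reader might infer that the 14-day wording hides later fatigue. It does not. Completion is also reported daily and weekly, MRT Data Analysis counts EMAs answered, messages viewed and days of engagement without a 14-day limit, and the diary items come at the end of the study. One burden item asks whether motivation to respond fell over the weeks. Only the overall percentage and the text survey carry the wrong period, which looks carried over from Aim 1.
- **Triggering.** The urge-to-drink item is asked at each decision point and again 15 minutes after randomization, with a no-message comparison. This bears directly on triggering by message type. It is still not a rating of the messages.
- **Two instruments or one.** The diary items on embarrassment, enjoyment, stress and irritation touch the emotional-response and satisfaction domains of the text survey. The two may be the same instrument; the text does not say.
- **Earlier message feedback.** In Aim 2, "Components will be refined via iterative cycles of user feedback collected via focus groups with 30 women". That work comes before the MRT and cannot show how women found the messages over 28 days.

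Asking burden items once at the end is also a defensible choice in a Stage I pilot. That does not settle who is asked, or where message acceptability is measured.

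**Conclusion.** The firm error is the 14-day period: it conflicts with the 28-day MRT and, taken literally, limits two primary-goal measures to half of the decision points.

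The other two parts are gaps in specification. As written, the 12 items reach only women still responding on the last morning, and none of them rates the messages. Whether the follow-up survey or interview fills these gaps cannot be judged from the documents. It would go too far to conclude that message acceptability is unmeasured or that the reported ratings will be biased by a known amount. The direction of bias depends on burden contributing to stopping, and its size is unknown. The 0.12 points per missing woman is exact for 50 women on a 1 to 7 scale, but the numbers missing are assumed. With no acceptability threshold in the plan, no changed decision is claimed.

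The point is worth correcting because it concerns a primary goal and costs little. It does not call the design into question.

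**What to change.** 1. In Feasibility and Acceptability Outcomes, change both 14-day timings to the end of the 28-day MRT, and state whether the text survey and the diary items are one instrument or two.
2. Keep the 12 items in the final diary. Through the already paid follow-up survey, offer the same items to every woman who started the MRT and did not answer that diary, including those counted as dropped for non-response. Exclude women who withdrew agreement to contact or were unenrolled for fraud.
3. Add a short rating of each message type (for example helpful, relevant, triggering) to the follow-up survey for all women who started. If the survey or interview already has one, say so.
4. State what the follow-up survey and interview measure, when they are given and to whom.
5. In MRT Data Analysis, report the number answering out of the number who started, split by diary and follow-up, with item means and bounds that set missing answers to 1 and to 7.

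The cost is a few sentences and a slightly longer survey. Non-answerers would respond in a different mode and after longer recall; follow-up timing is not stated, so how much longer is unknown. Contacting and paying women counted as dropped may need an ethics or consent amendment. Some non-response will remain among women who were silent through five reminders, which is why the bounds are needed. Women who answer the final diary still give the same 12 ratings.
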